In summary, there is no current effective approach to prevent GDM-related fetal overgrowth. We demonstrated that choline sufficiency was critical for restoring normal placental transport and preventing fetal overgrowth in GDM mice. If similar effects of choline could be validated in humans, the practical impact would be remarkable because currently less than 10% of pregnant women in the U.S. consume the recommended 450 mg/d Adequate Intake of choline (47). Choline is readily available in common foods such as eggs, beans, and meat and is easy and safe to provide via a choline-rich diet or choline supplements. When used in clinical trials, choline supplementation was well tolerated and was not associated with any serious adverse events.

STUDY OBJECTIVES

Specific Aim 1: Determine the effect of MCS during pregnancy on birth weight in GDM.

Specific Aim 2: Determine the influence of MCS on macronutrient transport and epigenetic modifications in the placenta and cord blood.

HYPOTHESIS

Aim 1: We hypothesize that the choline group would have lower birth weight and fewer LGA neonates than the non- choline group.

Aim 2: We hypothesize that the choline group would reduce placental transport and increase DNA methylation of metabolic genes.

STUDY DESIGN

Subjects: A convenient sampling methodology will be adopted. We will recruit pregnant women diagnosed with GDM during the second trimester of pregnancy on a rolling basis. Block randomization will be conducted based on treatment methods (i.e. insulin therapy, oral hypoglycemics, or diet only) to randomly assign participants to the intervention and control groups. Recruitment will be conducted using the following methods: (i) study flyers will be posted

at the prenatal clinic; (ii) the principle investigator and her fellows will identify pregnant women who are potentially eligible by reviewing medical records. All these patients are routinely seen by members of the MFM team fellows. The PI or co-I will introduce the study to potential participants.

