Eligibility Criteria: The inclusion criteria include GDM pregnant women before gestational week 28. GDM is diagnosed with the 2-step process: blood glucose higher than the 140 mg/dL cut-off value after 50 g non-fasting 1-hr and 100 g 3-hr oral glucose challenges. Pregnant women are qualified to participate if they are English- or Spanish- speaking, over 18 years of age, having singleton pregnancy, intending to deliver their babies at Maimonides and are without any of the conditions listed in the exclusion criteria. Exclusion criteria include pre-existing hyperglycemia, diabetes, cardiovascular conditions and liver disease prior to pregnancy. Patients may choose to participate in the study and not donate a biopsy of their placenta or umbilical cord. Patients who desire stem cell donation or storage will not be able to donate a biopsy of their placenta or umbilical cord. These patients will not be excluded from the primary analysis.

Design and Data Collection Procedures:

All interaction with participants will occur at Maimonides while sample analyses will occur at Brooklyn College (where the co-I's lab is located). The PI or co-I will obtain written informed consent from the pregnant women before study entry. Randomization will be done by pharmacy after patient signs consent. It will be block randomization of 10 patients. After randomization, the PI or co-I will provide the participant in the intervention group with choline supplement pills containing 500 mg of choline bitartrate (235 mg choline, Douglas Lab). The participant will consume 2 pills per day to obtain 470 mg choline for 8 weeks. The recommended intake of choline in the form of Adequate Intake (AI) is 450 mg/d for pregnant women and the Tolerable Upper Intake Level (UL) is 3500 mg/d. Since less than 10% pregnant women reach the AI of choline intake and the upper quartile of choline intake is below 900 mg/d (48). The dosage we provide plus the habitual intake of choline in these pregnant women will fall between the AI and UL, i.e. sufficient but not exceeding the limit. The participants in the control group will receive a placebo that contains corn oil. Both groups will also receive standard prenatal multivitamins and 200 mg/d DHA provided by the study group. We will provide the participants with 5 weeks supply of supplements and we will verify their compliance during the time with daily check-off logs of supplement consumption and leftover pill count during their next visit.

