Anthropometric measurements and blood collection: We will measure the participants' weight and height using a medical weighing scale with mechanical height rods during the visits. To minimize food-related concentration differences in plasma biomarkers, participants will be instructed not to consume food for at least 4 hours before their blood draw in the morning. This is a standard recommendation for prenatal visits and is considered as safe (52, 53). We will also have preventative measures such as an examination bed to rest in and juices, food, and water should the women need them. About 20 mL of fasting venous blood will be drawn from each participant during the visits by a fellow/resident/nurse. Blood samples will be collected into one EDTA blood collection tube and one serum separator tube and centrifuged to obtain plasma, buffy coat, and serum. Samples will be processed and stored at -80°C at Brooklyn College until being used for analytical measurements.

Blood glucose management: We will obtain information about fasting glucose, hemoglobin A1C, medication and insulin therapy from medical charts of the participants.

Birth information and sample collection at delivery: The participants will notify the PI or co-I when they are admitted to the birth center by phone. We will also send them reminders as their due dates are approaching. In addition, **the birth center medical staff will be given a list of participant names, thus they will also contact the PI or co-I if a participant checks in when none of the study staff is on site.** The research team will be available 24/7. Once the baby is delivered, we will collect two tubes of cord blood to retrieve serum, plasma, and buffy coat. We will measure the size and weight of the placenta and process the placenta using the following method: full-thickness placental biopsies will be obtained using a 6-mm Keyes punch and stabilized in RNeasy[®] (for RNA), or frozen in liquid nitrogen (for other purposes). Samples will be transported to the co-I's lab for long-term storage at -80C before use.

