Sample Size: We anticipate a 10% dropout rate due to reasons such as participants moving out of the city, pre-term deliveries, or missed placental collection. Therefore, we expect to have at least 27 sets of complete data in each group. A statistical power analysis was performed for sample size estimation accounting for rates of dropout and missing data, based on data from a randomized controlled trial of choline supplementation which demonstrates that 2 x recommended intake of choline for 12 weeks is sufficient to increase plasma choline and alter placental global DNA methylation. The initial sample size of n=30/ group will allow detection of a >20% difference in birth weight, plasma choline and placental DNA methylation at $\alpha < 0.05$ and power = 80%.

Expected Outcomes: The successful completion of this study will provide valuable insights into the use of choline supplement as a modifier of placental macronutrient homeostasis in GDM to improve fetal growth outcomes.

Timetable:

	Quarter 1	Quarter 2	Quarter 3	Quarter 4
Participant Recruitment	n = 20	n = 20	n = 20	
Sample and Data Collection				
Choline measurements		Aim 1	Aim 1	Aim 1
Gene expression and epigenetic measurements		Aim 2	Aim 2	Aim 2
Data analysis				Both Aims
Result dissemination				Both Aims

We expect to complete recruitment by the end of the third quarter and complete dietary record, clinical information, and biosample collection in the middle of the fourth quarter. We will start analytical measurements once we obtain at least a third of the samples. We expect to complete analytical measurements by the end of the year. We will analyze and disseminate data in the last quarter.

Data Safety Committee Team Plans:

Randomization is a block randomization of 5 patients. After every block of randomization, the research team with a pharmacist and at least one external physician outside of the research team [[name]] will analyze the data to ensure that there are no unanticipated adverse effects via ultrasound fetal growth patterns. If unanticipated effects are found, we will report to IRB as per policy.

REFERENCES

1. Ferrara A. Increasing prevalence of gestational diabetes mellitus: a public health perspective. *Diabetes Care*. 2007;30 Suppl 2:S141-6. doi: 10.2337/dc07-s206. PubMed PMID: 17596462.

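### The only safety review is timed by randomisation blocks and looks only at ultrasound growth; it does not use birth weight, and no review is planned after the last block

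*Combined protocol and SAP*

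**What the plan says.** The safety plan is one short paragraph under Data Safety Committee Team Plans. It opens with "Randomization is a block randomization of 5 patients". It then sets the timing and membership: "After every block of randomization, the research team with a pharmacist and at least one external physician outside of the research team". This group examines the data to ensure that there are "no unanticipated adverse effects via ultrasound fetal growth patterns", and anything unanticipated goes to the IRB. The paragraph gives no interval between the filling of a block and its review, and mentions no review after the final block or after delivery.

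Other sections bear on this:

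- **Randomisation.** Design and Data Collection Procedures gives a different block size: "It will be block randomization of 10 patients". The Subjects paragraph of Study Design bases the blocks on three treatment categories (insulin, oral agents, diet alone).
- **Follow-up.** Women are enrolled at a 28-week visit, take the supplement for 8 weeks and have a last antenatal study visit at 36 weeks. Eligibility Criteria puts entry before 28 weeks.
- **Data collected.** The text lists a questionnaire, dietary and activity recalls, weight, height, blood, and placenta and cord blood at delivery. For chart data it says: "We will obtain information about fasting glucose, hemoglobin A1C, medication and insulin therapy from medical charts of the participants". Birth weight and LGA are compared between groups under Data Analysis, Aim 1.
- **Size and pace.** Sample Size gives "The initial sample size of n=30/ group", and the Timetable gives 20 recruits in each of three quarters.

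**The concern.** The Aim 1 hypothesis is that choline lowers birth weight, so slowing growth too far is the foreseeable harm. The sponsor evidently saw this, since fetal growth is what the review watches. Three features limit what the review can detect.

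First, the trigger is enrolment and not follow-up. A review held when a block fills sees its newest members with almost no exposure, and when enrolment stops the reviews stop too.

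Second, detection is confined to ultrasound. Birth weight is the most direct measure of the harm, but the review is not said to use it.

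Third, the number of reviews cannot be worked out from the text.

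At stake is whether a growth problem would be noticed while women are still taking the supplement, and whether anyone with a safety role would look at the births of the last women enrolled.

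**Working it through.** **Inputs from the documents.** 30 per group; 20 recruits per quarter for three quarters; entry at 28 weeks; 8 weeks of supplement; block size 5 or 10; three treatment categories; collection to be complete by mid-quarter 4.

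**Assumptions, not in the documents.** A 13-week quarter with uniform accrual; delivery at 37–40 weeks; the last block filling with woman 60; the review held promptly after that.

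**Plan's own figures.** 3 × 20 = 60 = 2 × 30, and 30 × (1 − 0.10) = 27 complete sets per group. Both reproduce.

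**Accrual rate.** 20 / 13 = 1.54 women per week, so woman 60 enters at week 39. A single stream of blocks ends there with either block size (12 × 5 or 6 × 10).

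**Women still on supplement at the last review.** 8 weeks × 1.54 = 12.3, about 12 of 60 (21%). This needs no assumption about delivery.

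**Births still to come.** Weeks from entry to delivery × 1.54:

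| Scenario | Weeks | Births outstanding |
|---|---|---|
| Entry 28, delivery 37–40, prompt review | 9–12 | 13.8–18.5 (23–31%) |
| Same, review 4 weeks after last block | 5–8 | 7.7–12.3 |
| Entry 24, delivery 37–40, prompt review | 13–16 | 20.0–24.6 |

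Counting evenly spaced entries instead gives 14–19 in the first row and 8–13 in the second. By the same count, 41–46 births have already happened at the last block review, and the review as written does not use their birth weights.

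**Timetable cross-check.** Mid-quarter 4 is 6.5 weeks after the last enrolment, which would leave 6.5 × 1.54 = 10 births. But a woman enrolled at 28 weeks would then be at 28 + 6.5 = 34.5 weeks, before her 36-week visit. The timetable and the visit schedule do not fit together, so this figure is not a reliable lower bound.

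**Number and timing of reviews.** Blocks of 5 give 60 / 5 = 12 reviews and blocks of 10 give 60 / 10 = 6. If blocks run within the three categories:

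- The first full block can come as late as woman 3 × 4 + 1 = 13 (week 13 / 1.54 = 8.5) or woman 3 × 9 + 1 = 28 (week 28 / 1.54 = 18.2).
- Final blocks may stay unfilled. Leftovers are at most 4 per category with blocks of 5 and 9 with blocks of 10. Their sum must be a multiple of the block size, because 60 is. So up to 10 women (largest multiple of 5 not above 12) or 20 women (largest multiple of 10 not above 27) could sit in blocks that never trigger a review.

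**The case against.** **Scan data.** A reader might infer that ultrasound data are never gathered, because the collection sections do not mention scans. The documents do not support that. The safety paragraph itself commits the team to using scans, the women are in routine care with the clinical team, the Timetable text refers to collecting clinical information, and the design figure and any data collection tools are not visible. What can be said is that the source, schedule and abstraction of scans are not described. That is mostly missing detail.

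**First review.** A reader might also infer that no woman is near term at the first review, since a single stream fills a block of 5 in 3.25 weeks and a block of 10 in 6.5. With blocks inside treatment categories, the first full block could come at week 18.2, when the earliest women would already have delivered. The inference does not hold.

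**The birth count.** It depends on assumptions, and the wording could allow a review after a block's data have matured. This stands: the count must be given as a range. No lag is stated, however, and even an assumed 4 weeks leaves about 8–13 births outstanding.

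**Usefulness of a late review.** A single review after the last delivery cannot protect anyone still on supplement, and the final analysis will see all the births. This also stands, and it is why reviews should continue between the last randomisation and the last delivery. Over the 8 weeks after week 39, about 8 × 1.54 = 12 further births would accrue while the last women are still being supplemented.

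**Background safety.** The protocol describes choline as well tolerated. That is a reason for a light review, but not for one that stops at the end of enrolment.

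**Conclusion.** The concern holds in this form: the only safety review is tied to the filling of blocks, detects harm only through ultrasound growth, does not use birth weight, and is not planned to continue after the last block. At a last review in week 39, about 12 of 60 women have not completed the supplement, and about 14–18 births are outstanding. The first figure rests on uniform accrual and a prompt review; the second also needs entry at 28 weeks and delivery at 37–40 weeks, and moves to roughly 8–13 or 20–25 under the alternatives shown. If blocks run within categories, the last full block need not coincide with woman 60, so neither figure is fixed.

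The number and timing of reviews are undefined until the block-size and stratification passages are reconciled. This should be corrected. It does not show that the trial is unsafe or that scans will be missing.

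**What to change.** 1. Reconcile the block size (5 or 10), state whether blocks run within the three treatment categories, and say what triggers a review when a block does not fill.
2. Keep the block reviews, but state that they continue after the last randomisation until the last woman has completed supplementation and delivered, with a closing review then.
3. Have each review also see accrued birth weight for gestational age and any maternal or neonatal adverse events in the chart.
4. Let only the pharmacist and the external physician see data by arm. Birth weight is the Aim 1 outcome, and the research team should not see it by group during the trial.
5. Add the date and estimated fetal weight of routine growth scans to the chart abstraction already planned for glucose data.

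The cost is one or two extra meetings, some added abstraction and the work of keeping by-arm birth weights from the research team. Adverse-event capture is a real addition, because no recording of such events is described at present. No extra scans are needed, and no threshold or stopping rule is proposed.
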